The statistical hypothesis of interest is whether a mean change in weight or serum levels of POPs is detected at six months from the baseline. $H_0: \delta_I - \delta_P = 0$ vs $H_a: \delta_I - \delta_P > 0$, testing whether the mean change in weight or serum levels of POPs differs (mean change: δ , between the groups; δ_I , intervention group; δ_P , placebo group). The null hypothesis denotes no mean difference between the groups, and the one-sided alternative hypothesis denotes a difference between the groups, with the intervention group having a greater reduction in weight or serum levels of POPs over the course of the trial.

We plan to recruit and screen PBB registry participants, to enroll 120 participants into the trial. Our goal is to have 100 participants complete the 6-month trial duration. These estimates are based on the power analyses described here:

Power Analysis: The primary objective is to determine if the use of Orlistat results in weight loss in this population. Previous studies have shown an average of 2 to 3 kg weight difference between the intervention and placebo groups [16]. Assuming a standard deviation for weight change of 5 kg, we would have adequate power (80%) to detect a 2-3 kg difference ($\alpha=0.05$; $\rho=0.5$) in weight with a sample size of 50 in each group. Power analyses were performed in PASS 13 software [17].

The secondary endpoint is the change in serum concentrations of PBBs, PCBs, DDE, and PBDE at six months from the baseline. For the outcome of change in serum POP levels, we based our sample size estimations on the historical PBB data for PBB registry participants with at least 2 measurements within a year and the pilot data from Jandacek et al [18]. We estimate that the variance of the differences in PBB levels is expected to be between 0.1 and 0.2 log parts per billion (ppb) (σ^2_{diff}). We have used the pooled variances for our power calculations. From our historical data, we expect a 1% reduction in PBB levels due to the natural course of exposure. A sample size of 50 in each group, would provide at least 80% power to detect a mean change in log PBB levels of -0.1 and -0.2 log ppb with a significance level of $\alpha=0.05$.

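### The plan claims at least 80% power for PBB changes of -0.1 and -0.2 log ppb, but its own variances give only about 30% to 47% at -0.1

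*Combined protocol and SAP*

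**What the plan says.** The claim is in the Power Analysis part of the Statistical Analysis section. From registry members with repeat measurements and a published pilot trial, the plan estimates that "the variance of the differences in PBB levels is expected to be between 0.1 and 0.2 log parts per billion (ppb"), gives this the symbol sigma-squared with subscript diff, and adds: "We have used the pooled variances for our power calculations". It then says of the secondary endpoint: "we expect a 1% reduction in PBB levels due to the natural course of exposure". It concludes that 50 per group "would provide at least 80% power to detect a mean change in log PBB levels of -0.1 and -0.2 log ppb", at a significance level of 0.05.

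The hypothesis at the start of the section is a between-group contrast of mean changes, and there "the one-sided alternative hypothesis denotes a difference between the groups" in favour of Orlistat. The Statistical Modeling paragraph puts PBB on the natural-log scale. The text after the power statement plans 60 recruits per group to allow for 20% attrition, and concedes that the variance estimates rest on small samples.

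**The concern.** A variance of 0.1 to 0.2 is an SD of 0.32 to 0.45. An effect of 0.1 is then less than a third of an SD, and 50 per arm is far too few to detect that with 80% power. The stated inputs and the stated power stand in the same paragraph and cannot both be right.

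PBB is formally the secondary endpoint, but it is the scientific reason for the trial: the primary objective asks whether weight loss comes with a lower body burden of PBB and other POPs. On the natural-log scale, -0.1 is about a 10% reduction (1 - e^-0.1 = 9.5%). A reader who trusts the 80% could take a null PBB result as evidence against a reduction of that size. On the stated variances, the design would miss it more often than not.

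**Working it through.** **Inputs** (all from the Statistical Analysis section)
- n = 50 per arm, equal allocation.
- Variance of change v = 0.1 to 0.2, so SD = 0.316 to 0.447.
- Effect d = 0.1 and 0.2 log ppb.
- Alpha = 0.05. The stated alternative is one-sided; two-sided results are also shown.

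**Formula.** SE of the between-arm difference in mean change = sqrt(2v/n). Approximate one-sided power = Phi(d/SE - 1.645).
- v = 0.1: SE = sqrt(0.2/50) = 0.063. At d = 0.1, d/SE = 1.58 and power = Phi(-0.06) = 47%.
- v = 0.2: SE = sqrt(0.4/50) = 0.089. At d = 0.1, d/SE = 1.12 and power = Phi(-0.53) = 30%.

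Noncentral-t results:

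| Effect | Variance | One-sided | Two-sided |
|---|---|---|---|
| -0.1 | 0.1 | 47% | 35% |
| -0.1 | 0.2 | 30% | 20% |
| -0.2 | 0.1 | 93% | 88% |
| -0.2 | 0.2 | 72% | 60% |

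The plan does not say which variance goes with which effect. If they are paired in order (-0.1 with 0.1, -0.2 with 0.2), neither reaches 80%: 47% and 72% one-sided.

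**What 80% would need**
- Detectable difference = (1.645 + 0.842) x SE = 0.157 (v = 0.1) to 0.222 (v = 0.2) one-sided. As reductions, 1 - e^-0.157 = 15% and 1 - e^-0.222 = 20%. Two-sided: 0.177 to 0.251, or 16% to 22%.
- Sample size for -0.1: 124 to 248 per arm one-sided, 157 to 314 two-sided.
- Largest variance giving 80% at -0.1 with 50 per arm: 0.040 one-sided (SD 0.20), 0.032 two-sided.

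**Attempts to reproduce the claim at -0.1** (one-sided, variance 0.1 / 0.2)
- All 60 recruits per arm analysed: about 53% / 34%.
- Baseline-adjusted comparison, assumed correlation rho = 0.5 (variance x 0.75): 57% / 36%.
- The plan's random-intercept model with common baseline and three visits: 58% / 37% at rho = 0.5, 65% / 42% at 0.3, 49% / 31% at 0.9. The plan gives rho = 0.5 for weight only and none for PBB, so these are assumptions.
- The same model at rho = 0: SE = sqrt(1.6 x (v/2)/50) = 0.040 / 0.057, so power = Phi(2.50 - 1.645) = 80% / Phi(1.77 - 1.645) = 55%. Zero within-person correlation is not credible for a persistent chemical, and the upper variance still fails.
- Within-arm test of change from baseline, n = 50: 71% / 47%. This is not the stated hypothesis.
- All 100 completers as one sample: 93% / 72%. This does not compare the arms.
- Net effect of -0.09, if -0.1 is the Orlistat-arm change and placebo falls by 1% (ln 0.99 = -0.01): 41% / 26%.

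**Reading 0.1 to 0.2 as SDs.** With SD 0.2, SE = 0.2 x sqrt(2/50) = 0.040 and d/SE = 2.5. One-sided power at -0.1 is 80.4% by the normal formula and 79.9% by the noncentral t; two-sided it is about 70%. The other three combinations are near 100%. So the least favourable corner of the SD reading lands on the stated 80%.

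**The case against.** The strongest reply is that the arithmetic may be right and only the label wrong. The plan gives the quantity in log ppb, the unit of an SD (a variance would be in squared units), and the SD reading returns the stated 80% at its worst corner. If so, the design does have about 80% one-sided power at -0.1, and the 30% to 47% figures describe a slip of wording. That is plausible and the documents cannot exclude it. But the text calls the quantity a variance by word and by symbol, and then says that pooled variances were used, so as written the power does not follow.

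Several further points stand in part:
- The claim is partly met: -0.2 with variance 0.1 passes under one- or two-sided testing. With the mixed model at rho = 0.5, -0.2 passes one-sided across the whole variance range (98% and 84%). The firm failure is at -0.1.
- PBB is the secondary endpoint, and the weight calculation is separate.
- The plan admits much uncertainty about the variances. That caveat is about whether 0.1 to 0.2 is right; it does not correct the power calculated from those values.
- Nothing in the documents says how a null PBB result will be read, so the consequence is a risk and not a stated intention.

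**Conclusion.** The concern holds. Taking 0.1 to 0.2 as the variance of change, as the plan states, 50 per arm gives 30% to 47% power at -0.1 one-sided (20% to 35% two-sided), and at least 80% in only one of the four effect-variance combinations. This rests on a between-arm two-sample comparison of change at alpha 0.05 with 50 completers per arm. Baseline adjustment or the three-visit model raises the figures, but at any credible within-person correlation -0.1 stays well below 80%.

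A variance/SD mix-up is the likeliest explanation, though unconfirmed. Even on that reading the claim at -0.1 with SD 0.2 needs a one-sided test and a full 0.1 difference between arms: a net effect of -0.09 would give Phi(0.09/0.040 - 1.645) = 73%.

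**What to change.** First check the historical registry data and the power-software input to establish whether 0.1 to 0.2 is a variance or an SD. Then correct the sentence accordingly:

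- **If variances:** replace the power claim with a statement that 50 per arm gives 80% power for a between-arm difference of about 0.16 (variance 0.1) to 0.22 (variance 0.2) log ppb at one-sided 0.05, that is, a 15% to 20% reduction.
- **If SDs:** change the label, symbol and pooled-variance sentence to SD, and state that -0.1 with SD 0.2 has 80% power only one-sided (about 70% two-sided).
- **In both cases:** state that the effect is the difference between arms net of the expected 1% decline, and that alpha 0.05 is one-sided. If the calculation used the mixed model, state the within-person correlation assumed for PBB.

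The cost is wording in one paragraph and no extra participants. In the variance case the stated sensitivity for PBB becomes less favourable.

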Orlistat is an over-the-counter product approved by the FDA for weight loss and works by increasing excretion of fat into the stool. Since PBB is stored in body fat, we hypothesized that Orlistat may reduce the body burden of PBB and other POPs. The proposed study is a randomized, placebo-controlled trial of Orlistat (at the dose available over-the-counter) plus diet and exercise for 6 months in a population with elevated PBB levels. Participants will be healthy overweight adults and Orlistat will be taken as directed for the approved indication (weight loss). We will follow all FDA-approved eligibility criteria and not enroll anyone with contra-indications to taking the drug. In addition, we will screen individuals for liver, kidney, or thyroid abnormalities, excluding anyone with abnormal values. We will repeat clinical laboratory tests at the conclusion of the trial (at 6 months). The primary outcome is weight loss and the secondary outcomes are blood levels of PBBs and other POPs. Sixty individuals will be included in each arm, with the aim of fifty participants completing 6 months of participation in each arm (100 total).

PROTOCOL SUMMARY

Figure 1: Schema

INTRODUCTION & BACKGROUND

In 1973, the Michigan Chemical Company accidentally shipped FireMaster, a brominated flame retardant mixture in place of a nutritional supplement for livestock feed. This introduced polybrominated biphenyls (PBB) into the Michigan food chain, ultimately exposing millions of Michigan residents, and resulted in one of the largest chemical exposure incidents in US history. To evaluate long-term health effects of exposure, the Michigan PBB Research Registry was established in 1976. The Registry is a multigenerational cohort with over 7,000 individuals ever enrolled, and includes those exposed during the contamination incident as well as subsequent generations, as PBB can be transferred from mother to child in the womb and through breastfeeding. Health-related research has been ongoing with this cohort for almost forty years and evidence to date of adverse health outcomes associated with PBB exposure includes increased risk of breast cancer, lymphoma, earlier age at menarche, increased miscarriages and lower estrogen levels among females, and more urogenital problems among males. Increased risks of thyroid dysfunction have also been found among men and women.

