Orlistat is an over-the-counter weight-loss aid that preferentially reduces body fat compared to diet and exercise alone. Our primary outcome is weight loss. Our secondary outcome is the change in concentration of chemicals that are stored in body fat (POPs). We hypothesize that the Orlistat group will lose more weight than the placebo group and because Orlistat preferentially reduces fat, that the weight loss in the Orlistat group will be accompanied by a reduction in serum levels of fat-soluble chemicals (POPs). Eligible individuals (using stricter criteria than recommended by FDA), will be randomized to Orlistat or placebo taken 3x daily with food. Both groups will receive multivitamins and a program of diet and exercise for six months.

Objectives:

To explore whether weight loss associated with Orlistat has a secondary effect of reducing blood levels of PBB and other POPs

Endpoints:

Primary Endpoint: Weight loss

Secondary Endpoint: Change in serum concentrations of PBBs, PCBs, DDE, and PBDE.

Study Population:

We will conduct this study among individuals exposed to polybrominated biphenyls (PBB) as the result of an industrial accident. We estimate we will need to enroll approximately 120 individuals into the trial to have 100 complete the 6-month trial duration. Healthy men and women, aged ≥ 18 with a BMI ≥ 25 and at high risk for a PBB level ≥ 1 part-per-billion or a recently measured PBB level ≥ 1 part-per-billion will be screened for additional health-related eligibility criteria. We will NOT enroll individuals with contra-indications for Orlistat and will have more stringent inclusion criteria than recommended by the FDA for Orlistat.

Description of Sites/Facilities

Participants will be enrolled by telephone from Emory University or enrolled in-person by Emory staff in Michigan.

Enrolling Participants:**Description of Study Intervention:**

Random assignment to Orlistat at the over-the-counter dose (60 mg capsule, up to three times daily with fat-containing meals) or placebo capsule. Diet and exercise plus a daily multivitamin will also be recommended and monitored for both groups.

Study Duration:

Approximately three years.

Participant Duration:

Six months

Figure 2: Schedule of Activities

Procedures	STUDY CALENDAR				
	Screening		Time (months) ± 2 weeks		
	1	2	Enroll ment	3	6
Review previously collected data for provisional eligibility	X				
Informed Consent		X			
Telephone screen for additional eligibility criteria		X			

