After accounting for 20% attrition (based on 18% in Jandacek), our goal is to recruit at least 60 participants per group. The sample size projections are, in large part dependent on the estimated variances. Given the small sample sizes on which we have to estimate the anticipated variance, there is much uncertainty in the sample size needed. However, given the statistically significant findings of increased excretion of PCBs with only 14 individuals in each group consuming potato chips with artificial fat [18], we feel that 50 individuals in each group comparing Orlistat to placebo is reasonable based on all available preliminary data.

Data Management: Analysis variables will be captured from the study measures (anthropometric measures, blood levels, diet assessment, and physical activity assessment). Data will be collected and coded systematically, reviewed periodically for quality control, logical checks, data entry errors, missing or invalid values and logical inconsistencies among related questions will be checked. Plausibility of outliers will be examined. All data related changes, including changes to respective datasets will be documented electronically. Analytic datasets will be created to address specific study aims. Data dictionaries will be created. All data files will be maintained on a password-protected network system. Original and back-up datasets are stored on a secured network server.

Data exploration and will include the following: 1) determining whether the shapes of continuous distributions indicate that transformations are needed, 2) ensuring that the underlying assumptions of statistical analyses are satisfied (normality, linearity and homogeneity of variance), 3) identifying potential collinearity problems, 4) identifying potential outliers that require further investigation, and 5) exploring bivariate and unadjusted associations with the endpoints and reviewing potential confounding variables. These will be considered prior to constructing models to address our study hypothesis. Descriptive statistics will include means, medians, and percentiles as appropriate for each variable of interest.

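### Sixty per arm with 20% attrition leaves 48 completers per arm (96 in total), not the 50 per arm (100) at which the plan states its power

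*Combined protocol and SAP*

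**What the plan says.** **Enrolment and attrition.** The paragraph after the power analysis, under Statistical Analysis, begins "After accounting for 20% attrition" and continues "our goal is to recruit at least 60 participants per group". It gives 18% in the cited dietary intervention trial as the basis for the 20%, and ends: "we feel that 50 individuals in each group comparing Orlistat to placebo is reasonable".

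**Completers.**
- Opening summary: "Sixty individuals will be included in each arm, with the aim of fifty participants completing 6 months of participation in each arm".
- Study Overview, Study Population: "We estimate we will need to enroll approximately 120 individuals into the trial to have 100 complete the 6-month trial duration".
- Statistical Analysis: "Our goal is to have 100 participants complete the 6-month trial duration", from an enrolment of 120.

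**Power.** For weight, 80% power is stated for a difference of 2-3 kg "in weight with a sample size of 50 in each group". For log PBB the plan says: "A sample size of 50 in each group, would provide at least 80% power".

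**Margin and replacement.** Participant Selection, Population, sets enrolment at 20% above the final target. Participant Discontinuation or Withdrawal gives two replacement rules. Randomised participants who never receive the intervention may be replaced, with no threshold. Those who received it and then leave are not replaced unless withdrawals exceed the anticipated rate of approximately 20%.

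**The concern.** Three figures are tied together: 60 enrolled per arm, 20% lost, 50 completing. Any two of them fix the third, and the three stated values do not agree. The 50 matters because it is the only sample size at which power is given, for the primary endpoint and for the secondary one. If attrition turns out exactly as anticipated, the trial will appear to have missed its target of 100 completers, and no power will have been stated for the number that it actually has. The plan itself says that the sample size needed is very uncertain because the variances are poorly known, so the completer count should at least follow from the stated inputs.

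**Working it through.** **Inputs.** From Statistical Analysis: 120 enrolled (60 per group), 20% attrition based on 18%, 50 per group for power, SD of weight change 5 kg, difference 2-3 kg, alpha 0.05, rho 0.5, one-sided alternative. From Participant Selection: enrolment 20% above target. From Participant Discontinuation or Withdrawal: anticipated withdrawal of approximately 20%.

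**1. Reproducing the plan's 60.** Target x (1 + margin) = 50 x 1.20 = 60 per arm, and 100 x 1.20 = 120. This matches exactly, so the 60 follows the margin rule in Participant Selection. Allowing for attrition means dividing by the fraction retained: 50 / 0.80 = 62.5, not 60.

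**2. Completers from 60 per arm.**

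| Attrition | Per arm | Total |
|---|---|---|
| 20% | 60 x 0.80 = 48 | 120 x 0.80 = 96 |
| 18% | 60 x 0.82 = 49.2 | 120 x 0.82 = 98.4 |
| 16.7% | 60 x (50/60) = 50 | 100 |

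The break-even rate is 1 - 50/60 = 16.7%. The plan gives this rate nowhere, and it is lower than the 18% on which the plan relies.

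**3. Replacement.** If 24 of 120 treated participants withdraw, the rate is 24/120 = 20%. That does not exceed the threshold, so none need be replaced and 96 remain. If some of the 24 never received the intervention, they may be replaced and the shortfall shrinks. This is optional and does not apply to treated withdrawals.

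**4. Cost in precision and power for weight.** If dropouts contributed no data, the standard error of the group difference would grow by sqrt(50/48) = 1.021, that is by 2.1%.

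Power is from a two-sample t-test (noncentral t) with noncentrality d / (SD x sqrt(2/n)), 2n - 2 degrees of freedom and alpha 0.05. The plan does not say how rho was used, and the power paragraph does not state sidedness. Four versions are therefore shown: SD 5 kg with rho ignored, and SD 5 x sqrt(1 - 0.5^2) = 4.33 kg, which assumes a reduction of the kind that baseline adjustment gives, each one- and two-sided.

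| SD (kg) | Sides | Difference (kg) | Power at 50 | Power at 48 | Loss (points) |
|---|---|---|---|---|---|
| 5 | 1 | 2 | 63.4% | 61.8% | 1.5 |
| 5 | 1 | 2.5 | 79.9% | 78.4% | 1.5 |
| 5 | 1 | 3 | 90.9% | 89.9% | 1.0 |
| 5 | 2 | 2 | 50.8% | 49.2% | 1.6 |
| 5 | 2 | 2.5 | 69.7% | 67.9% | 1.8 |
| 5 | 2 | 3 | 84.4% | 82.9% | 1.5 |
| 4.33 | 1 | 2 | 74.2% | 72.6% | 1.5 |
| 4.33 | 1 | 2.5 | 88.9% | 87.8% | 1.2 |
| 4.33 | 1 | 3 | 96.4% | 95.8% | 0.6 |
| 4.33 | 2 | 2 | 62.8% | 61.0% | 1.8 |
| 4.33 | 2 | 2.5 | 81.6% | 79.9% | 1.6 |
| 4.33 | 2 | 3 | 92.9% | 91.9% | 1.0 |

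Losses are taken before rounding and run from 0.6 to 1.8 points.

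**5. Log PBB.** Reading the plan as a group difference of 0.1 or 0.2 with variance 0.1 or 0.2, one-sided power at 50 per group runs from about 30% (variance 0.2, difference 0.1) to 93% (variance 0.1, difference 0.2). Only one of the four combinations reaches the stated 80%. This reading does not reproduce the plan's calculation, so no loss is derived from it.

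**The case against.** The best case for the plan has four parts.

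- **The enrolment rule is stated and correct.** Enrolling 20% above target gives 120 for 100. This stands. It narrows the fault to treating that margin as cover for 20% attrition. It does not remove the fault, because the withdrawal section also treats approximately 20% as the anticipated loss.
- **The figures are hedged.** The completer numbers are mostly an aim or a goal, 60 is a floor, 120 is approximate in one place, and 20% is rounded up from 18%. This softens the tone. But the Study Population text is an estimate of the enrolment needed for 100 completers, and it falls short at 18% as well as at 20%.
- **Losing two participants per arm changes little.** This stands. With SD 5 kg and rho not used, the difference detectable with 80% power moves from 2.50 to 2.56 kg one-sided and from 2.83 to 2.89 kg two-sided, within the plan's 2-3 kg range each time. At 2 kg, power in that calculation is below 80% at both 50 and 48, so the gap does not decide whether the plan's power statement holds.
- **Dropouts are not wholly lost.** Participants who stop the drug are still asked for the 3- and 6-month blood draws, and the intention-to-treat mixed model can use partial data. This makes the losses above upper limits. It does not change the completer count, which is the quantity that the plan targets.

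A reader might infer that no withdrawal can be replaced below 20%. The documents do not support that, because untreated randomised participants may be replaced at any rate.

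**Conclusion.** The inconsistency is real and minor. At the plan's own 20% attrition, 60 per arm yields 48 completers per arm (96 in total), two per arm fewer than the number behind both power statements. Nothing in the documents reconciles the figures. The completer arithmetic needs no assumption beyond the stated attrition and no replacement of those who leave. The power cost for weight is an illustration: it assumes a two-sample t-test, one of the two treatments of rho, and no data from dropouts.

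Two stronger readings are tempting and should not be drawn. One is that this gap leaves the trial underpowered; a loss of under 2 points does not show that. The other is that power for log PBB falls by a similar known amount; the plan's calculation for that endpoint could not be reproduced, so no figure can be given.

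**What to change.** 1. In the attrition paragraph under Statistical Analysis, write: *Sixty per group with 20% attrition gives about 48 completers per group (96 total); 50 per group is reached only if attrition is at most 16.7%.*
2. In Study Overview, Study Population, change the estimate to: *enroll approximately 120 individuals, of whom about 96 are expected to complete at 20% attrition.*
3. Keep 50 per arm (100 in total) as the aim in the opening summary and in Statistical Analysis.
4. Rerun the plan's own power calculations for weight and log PBB at 48 per group, with the plan's rho and sidedness, and state the results beside those for 50.

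Enrolment stays at 120, and the margin rule and the replacement rules are unchanged. The cost is two wording edits and one rerun of existing calculations. The downside is a slightly less favourable completer number and power. Securing 50 completers instead would need 63 per arm (126 in total) at 20% attrition, or 50/0.82 = 60.98, so 61 per arm (122 in total), at 18%. Given the size of the effect, that is not proposed.
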